**Defining and operationalizing the denominator:**

- To determine if a patient has a diagnosis of one of the priority cancer types, use ICD-10 diagnosis codes: 15.0-16.99 (esophago-gastric) C17.0-C21.9 (small int. colorectal) C22.0-24.9 (hepatobiliary) C23-C25.9 (pancreas), C34-34.9: lung, C53.0-53.9 (cervix) C54-54.9 (uterine) and/or C56-57.9 (ovarian). When it comes time to execute, this list may be modified. CPT and procedure codes as well as EPIC operating room scheduling lists will be used to determine if a patient is scheduled for a priority surgery.
- Participants assigned to eSyM+ may be trained to use eSyM by their local clinic/study staff. Surgical patients may be trained to use eSyM at the time of surgical discharge (or at the site's discretion patients may receive training in how to use eSyM at a preoperative visit). Med Onc patients may be trained to use eSyM at the time of their first chemotherapy dose visit or at the time of a pre-treatment visit for chemotherapy teaching (at the site's discretion). Epic reports may also be used to identify eligible patients who are assigned or will be assigned to eSyM so that training of the eligible patients can be done by study research staff via telephone or email before or after beginning treatment or having surgery.
- Participants in the eSyM- cohort will meet priority population criteria and be seen at a participating site between 1/1/2018 and the site's eSyM go-live date. Participants in the eSyM+ cohort will meet priority population criteria and be seen at a participating site after their eSyM go-live date through March 31, 2024.

**Mode of Participation:** Patients will have a *choice* of their preferred mode of eSyM participation and switching can be accommodated. Patients with a smart phone will be offered that approach first, however all patients will be notified that access to eSyM is available as long as they can access the secure patient portal (MyChart). eSyM can be accessed securely through the MyChart portal on any web-enabled device. Alternatives to smart phone reporting include

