#### Activity 4c (Medical Record Abstraction)

- Patient identifier for all patients in the denominator cohort (eSyM users and non-users) - study ID # and/or encrypted MRN (collected via Epic and encrypted as needed by site study team)
- Patient study site ID for all patients in the denominator cohort (eSyM users and non-users)
- Patient zip code of residence (collected from Epic registration field)
- Patient DOB for all patients in the denominator cohort (eSyM users and non-users) – DOB can have encrypted birth month and day as described above under activity 3c.
- Patient vital status
- Patient demographic information, including sex, race, ethnicity, language, marital status, employment status, and education level
- Patient eSyM inclusion information, including cancer diagnosis data and/or procedure data
  - Cancer diagnosis code (ICD-10 codes), date and description
  - Complete Epic problem list
  - Procedure code (CPT code), date, description, and goal
  - Cancer staging code

- Treatment plan information, including start date, end date, intention
- Medications list
- Patient dates of service including surgery, chemo administration, follow-up appointments (collected via Epic) for all patients in the denominator cohort (eSyM users and non-users)  
Please see detail under Activity 3c.
- Study-outcomes collected via Epic including:
  - Hospital readmission rates within 90 days for surgical patients
    - Information will include visit dates, discharge diagnosis codes
  - Hospital admission rates within 90 days of chemotherapy for medical oncology patients.
    - Information will include visit dates, discharge diagnosis codes
  - Emergency department visits (including those that culminate in admission versus those that culminate in discharge) for surgical and medical oncology patients
    - Information will include visit dates, discharge diagnosis codes
  - Dates of chemotherapy administration

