 - Surg episode where its trigger event occurred after the patient experienced eSyM MO, but before eSyM Surg was rolled out in the patient's site.
 - For example, the 4th episode in the Figure (below) was before go-live of MO in this site and thus this episode is considered eSyM control data(eSyM-). While this patient did not experience the eSyM MO intervention at that time, this patient already experienced the eSyM Surg intervention (eSyM+) (see the 3rd episode in the figure). Therefore, we do not include the 4th episode as eSyM control (eSyM-) data but exclude it from the primary analysis.

[figure not shown]

- As sensitivity analyses, we will perform the analyses using the data consisting of only the first episode from each subject.

Occurrence of another trigger event during the follow-up of an episode:

- If another trigger event (Event B) occurs during the one-year follow-up period of a trigger event (Event A), the data collected after Event B will be included in the aggregation as data of the episode triggered by Event B, not by Event A (Figure below)

Example

Analysis Populations:

All eligible subjects accrued in this study will be included in the primary analysis. To investigate the impact of patient's engagement with eSyM on clinical outcomes, two additional analysis populations will be considered for secondary and exploratory analyses.

To this end, we consider 3 total groups for analysis:

- Group A: episodes where subjects engaged* with eSyM among the eligible episodes of eligible subjects observed in the eSyM intervention (eSyM+) period.
- Group B: episodes where subjects did not engage with eSyM among the eligible episodes of eligible subjects observed in eSyM+.
- Group C: eligible episodes of eligible subjects observed in the eSyM control (eSyM-) period

* Definition of episodes where patient engaged with eSyM: episodes where patient reports ePRO through eSyM at least once during the follow-up

Table 6 shows the details of each analysis population.

Table 6: Analysis Populations and Objectives

Analysis Population	Comparison	Objective	Notes
1) A+B+C	(A+B) vs. C (Primary analysis)	Estimating the effect of eSyM exposure in a future population similar to the entire study population	Exposed to eSyM vs. Unexposed to eSyM regardless of engagement with the exposure (Effectiveness) Clinical outcome data from all groups will be included in the analysis on the basis of the Intention-to-treat principle.

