2) A+C*	A vs. C (Pre-specified Secondary)	Estimating the effect of eSyM exposure in a future population that consists of patients who will engage with eSyM upon exposure.	Exposed to eSyM vs. Unexposed to eSyM conditional on engagement with eSyM (Efficacy) C* is a subset selected from C, so that the case-mix matches A (i.e., Engagement with eSyM). A and B are used to build the propensity score to select C*.
3) A+B	A vs. B (exploratory)	Estimating the effect of eSyM engagement in a future population similar to the study population if everyone engages, under the assumption that everyone in that population engages with eSyM upon exposure.	Engagement with eSyM vs. Unengagement with eSyM, conditioning on everyone being exposed to eSyM Propensity score weighting will be used to adjust for case-mix.
Data collected before go-live (eSyM-)		Data collected after go-live (eSyM+)	
C. Episodes under the control condition		A. Episodes under the intervention condition, where patient engaged with eSyM B. Episodes under the intervention condition, where patient did not engage with eSyM	

- 1) The primary analysis population consists of all eligible episodes under the intervention condition (A+B) (i.e., eSyM exposed) and all eligible episodes under the control condition (C) (i.e., eSyM unexposed).
- 2) The secondary analysis population consists of the episodes where patients engaged with eSyM (A) and the matched episodes during the pre-intervention period (C*). C* is a subset of C. In this analysis, we are interested in estimating the intervention effect among a subgroup of patients who will engage with eSyM if exposed. First, for MO and Surg, a propensity score model (a logistic regression model) to predict engagement with eSyM will be derived using the data from A and B. Next, for each subject in A and C, the predicted probability of engagement will be calculated using the derived propensity score model. The pre-specified variables used for the propensity score models are listed in **Table 7**. For each intervention episode in A, one control episode in C will then be matched, without replacement, based on their predicted probabilities of engagement, using the nearest neighbor matching method stratified by site. The matched dataset is then run through the same outcome model as the primary comparison.

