- 3) As exploratory analyses, we will compare A vs. B. Under the condition that the hospitals have switched on the eSyM system (i.e., everybody is exposed to the eSyM system), we are interested in estimating the effect of the eSyM engagement on the outcomes under the assumption that everyone engages with eSyM, compared to the case where no one engaged with eSyM in spite of eSyM exposure. A propensity score weighting will be used to adjust for the case-mix between engagement with eSyM and non-engagmenet with eSyM. We will build a propensity score model for MO and Surg, separately, using the data from A and B. The pre-specified variables used for the propensity score models are listed in **Table 7**. No outcome model will be involved in this analysis.

Table 7: Pre-specified variables included in the propensity score models

Variable	2) A vs. C*	3) A vs. B	Note
Goal of Chemotherapy (MO with curative goal, MO with palliative goal, Others)	X	X	Only the models for MO
Calendar Time (Secular trends) [continuous with natural cubic spline]		X	
Site (Treating Facility) (DFCI, MMC, DHMC, LCI, BAPT, WVU)	X	X	
Age (year) (fractional polynomials)	X	X	
Sex (male vs. female)	X	X	
Race/Ethnicity (white/non-Hispanic, black/non-Hispanic, Hispanic, Other/Unknown)	X	X	
Employment (Employed, disabled, retired, other)	X	X	
Marital status (married vs. not married)	X	X	
Rurality based on zip code (large metro, small metro, suburban, rural)	X	X	
Insurance type (Medicare only, Medicare and Medicaid, Medicaid only, Private, Other)	X	X	
Cancer type (GI, Gyn, Thoracic)	X	X	
Socio-economic status (quintiles by the zip code-based poverty level)	X	X	
Co-morbidity (Charlson comorbidity index from encounter diagnoses in the 12 months before the first eligibility date) (0, 1, 2+)	X	X	

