6.1. Outcomes and summary measures

The outcomes investigated in Aim 2c of the SIMPRO study are classified into four groups, depending on the data source and data collection schedule. **Table 12** shows the details of the groups and the disposition of each outcome in Aim 2c.

Table 12: Outcomes in Aim 2c		
Type	Outcome Type in the SIMPRO study	Example outcomes in Aim 2c
1	Measured at one single time point only either in post-intervention (the intervention condition) or in pre-intervention (the control condition) for all or selected subjects (patients or providers)	eSyM decline (1 st time)
2	Measured at multiple time points (periodically) only in post-intervention period for all or selected subjects (patients or providers)	eSyM logins per patient per month
		Frequency of patient eSyM reports with severe symptoms
3	Measured from selected subjects (patients or providers) at a single time point, which could be during the pre-intervention period or the post-intervention period. For some subjects, data may be collected at both periods.	PROMIS items (self-efficacy for managing symptoms, pain interference, fatigue, and physical function)
4	Measured periodically through the SW-CRT design from all eligible subjects.	MyChart activation (binary outcome)
		MyChart logins per patient per month

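### The engagement propensity models omit MyChart activation, so C* may not represent patients who would engage, and A vs C* is open to confounding of unknown size and direction

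*SAP*

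**What the plan says.** SAP 4.2 counts an episode as engaged under this definition: "episodes where patient reports ePRO through eSyM at least once during the follow-up". Group A is the engaged eSyM+ episodes, B the non-engaged eSyM+ episodes, and C the control episodes. The aim of A vs C* is stated as "we are interested in estimating the intervention effect among a subgroup of patients who will engage with eSyM if exposed".

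The method has three steps. First, "a propensity score model (a logistic regression model) to predict engagement with eSyM will be derived using the data from A and B", separately for medical oncology and surgery. Second, every subject in A and C receives a predicted probability of engagement. Third, each A episode is matched to one C episode by nearest neighbour within site, without replacement. No caliper and no portal requirement is stated. The matched data then go through the primary outcome model. The June 2024 addendum limits A and C* to first episodes and leaves Table 7 as it is.

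Table 7 ("Pre-specified variables included in the propensity score models") contains chemotherapy goal (medical oncology only), site, age, sex, race/ethnicity, employment, marital status, rurality, insurance, cancer type, zip-code poverty level and comorbidity. Calendar time is in the A vs B model only. Table 8, which defines the outcome model, has no portal variable either.

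The protocol (Activity 4, Mode of Participation) says that "all patients will be notified that access to eSyM is available as long as they can access the secure patient portal (MyChart". SAP Table 12 lists "MyChart activation (binary outcome" as a Type 4 outcome of Aim 2c, a type measured throughout the stepped-wedge design in all eligible subjects. Protocol section 12.0, Activity 4c, also collects "Patient demographic information, including sex, race, ethnicity, language, marital status, employment status, and education level"; language and education are not in Table 7.

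**The concern.** Portal access is the main gateway to engagement. Two controls with identical Table 7 values, one with an account and one without, receive the same score and are equally eligible for C*. Group A consists of people who did report through eSyM. The matching therefore aligns A and C* on demographic, socio-economic and clinical variables and leaves portal status free to differ. The outcome model does not correct this.

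If portal status predicts EDTR beyond those covariates, A and C* would differ in risk even if eSyM did nothing, and the difference would be read as an effect in would-be engagers. The exploratory A vs B analysis has the same gap and less protection, because it relies on propensity weighting alone with no outcome model. Table 13 reports usage rates both restricted and not restricted to MyChart patients, so the plan itself expects some eSyM-assigned patients to lack MyChart.

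**Working it through.** The plan gives no activation rate, engagement rate, sample size or power for A vs C*, so there is no figure to reproduce. What follows is an illustration on stated assumptions.

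**Inputs**
- Control EDTR risk by Day 30: 10%, within the 8% to 15% of SAP 4.7.
- Planned effect: 3 to 4 points (SAP 4.7).
- Portal activation before the trigger event: 60%, 75% or 90% (assumed).
- Odds ratio for EDTR, inactive versus active, given the covariates: 1.0, 1.5 or 2.0 (assumed).

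**Step 1: share of C* without an active portal (u).** If the Table 7 variables did not predict activation at all, u would equal 1 minus the activation rate: 40%, 25% or 10%. The SAP rule was simulated (score fitted in A+B, 1:1 nearest-neighbour matching without replacement, C as large as A+B, engagement requiring activation). Across weak to strong prediction of activation by the covariates, u was:
- 60% active: 36% down to 26%
- 75% active: 23% down to 16%
- 90% active: 9% down to 7%

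**Step 2: risk in each stratum.** With activation m, solve m × p_active + (1 − m) × p_inactive = 10% at the assumed odds ratio. For m = 0.75 and OR 1.5, p_active = 9.02% and p_inactive = 12.94%. Check: 0.75 × 9.02 + 0.25 × 12.94 = 10.0.

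**Step 3: spurious difference with no true effect**, taking A as all active: −u × (p_inactive − p_active).

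| Active | OR 1.5: risk gap | Spurious difference (points) | OR 2.0: risk gap | Spurious difference (points) |
|---|---|---|---|---|
| 60% | 12.24 − 8.51 = 3.73 | −1.0 to −1.3 | 13.84 − 7.44 = 6.40 | −1.7 to −2.3 |
| 75% | 12.94 − 9.02 = 3.92 | −0.6 to −0.9 | 15.25 − 8.25 = 7.00 | −1.1 to −1.6 |
| 90% | 13.72 − 9.59 = 4.13 | −0.3 to −0.4 | 16.90 − 9.23 = 7.67 | −0.5 to −0.7 |

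Example: 0.23 × 3.92 = 0.90. At OR 1.0 the difference is zero. If inactive patients have the lower recorded EDTR, the sign reverses.

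**Step 4: patients who activate once offered eSyM.** Suppose half of inactive patients do so. A then also contains patients who were inactive before the trigger, and only the gap in shares matters. In the weak-prediction case the shares in C* and A were 38% and 24% (60% active), 23% and 14% (75%), and 9% and 5% (90%). At OR 1.5 the difference is 0.14 × 3.73 = 0.5, 0.09 × 3.92 = 0.4 and 0.04 × 4.13 = 0.2 points. The bias is smaller but does not vanish.

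**Step 5: balancing pre-trigger status.** If A and C* have the same share of pre-trigger inactive patients, the gap in Step 4 is zero, and so is the bias from this source.

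**The case against.** Several stronger readings are tempting, and the documents do not support them.

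- *Controls without an account could never have engaged, so their engagement probability is zero and positivity fails.* Staff set patients up for eSyM, in-clinic completion is allowed and proxies may report (protocol, Activity 4). The SAP also plans to estimate the effect of eSyM on activation (6.2, Type 4). A control without an account might have opened one if offered eSyM.
- *C* consists mainly of such controls.* In the scenarios above they are a minority, 7% to 38%, on assumed rates.
- *The comparison is shown to be confounded.* Table 7 includes age, race, rurality, insurance and poverty level, and the outcome model adjusts again for some of these. Bias needs activation to predict EDTR after all that. This is plausible but not shown.
- *The protocol's 2016 web-access table supplies the missing rate.* It describes US adults' internet access, not MyChart activation at these sites.

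It can also be argued that leaving out a variable that eSyM may change is a sound choice. That holds for activation after the trigger event. It does not hold for status before the trigger, which eSyM offered at that trigger cannot have changed.

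A last objection stands in part. Type 4 measurement implies control data, but not that every control has a dated status before the trigger. The protocol lists MyChart activity under Activity 4a (app usage), not under the 4c record abstraction.

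**Conclusion.** The omission is certain from the text: neither the score models nor the outcome model contains portal status, although portal access is a stated condition of using eSyM and activation is planned for all eligible subjects. C* may therefore differ from A on the main gateway to engagement, and the Efficacy label is not secured.

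The consequence is a possible bias, with direction and size unknown. Under the assumptions above it ranges from nothing to about 2 points (0.3 to 1.3 at an odds ratio of 1.5; 0.5 to 2.3 at 2.0), and less if many inactive patients activate when offered eSyM. Against a planned effect of 3 to 4 points, that justifies a change. It concerns a pre-specified secondary and an exploratory analysis; the primary (A+B) vs C comparison does not use the score.

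**What to change.** Add MyChart activation status before the trigger event to both Table 7 models, and match A to C* exactly on it in addition to site. Do not use status after the trigger, which eSyM may change. Report activation in A, B, C and C*, with covariate balance after matching.

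Exact matching is preferable to restricting the analysis to prior portal users. Restriction would remove engagers who activated because eSyM was offered: about 24%, 14% and 5% of matched A at 60%, 75% and 90% activation, if half of inactive patients activate. It would also narrow the target population. With exact matching these patients stay in A and are paired with inactive controls.

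The cost is SAP wording, confirmation that dated pre-trigger status exists for controls, and possibly some lost matches. If the dates are unavailable, state the limitation and soften the Efficacy label. Adding language and education to Table 7 is optional and depends on their completeness, which the documents do not report.

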4.3. Description of the Study Participants and Characteristics of Eligible Episodes

Disposition of the study participants:

Following the CONSORT guideline,^{6,8} a CONSORT diagram will be generated to describe the patient population with descriptions of the numbers of participants.

Patient demographic and disease characteristics:

- Baseline patient characteristics and disease characteristics at the start of follow-up will be summarized using descriptive statistics by sequence (i.e., site).
- The unit of the analysis is not patient but episode. All eligible episodes eSyM- episodes will be included in this analysis.
- The same analysis will be performed for each of the two cohorts (MO and Surg).

The PRECIS score

The Pragmatic-Explanatory Continuum Indicator Summary (PRECIS) score will be calculated and reported.

4.4. Multilevel Generalized Linear Regression Analysis

The primary analysis for the outcomes in Aim 2 (Table 5) will be performed via multilevel generalized linear regression models (or generalized linear mixed-effects model; GLMM).⁹ The null hypothesis for the statistical test is no intervention effect on the outcome, which indicates that the regression coefficient for the intervention indicator variable is zero. The intervention effect will be summarized in both absolute and relative terms (CONSORT Checklist Item 17b).⁷

Followings are specifications of the GLMM for the primary and secondary analyses.

- Link function
 - For binary outcomes, the logit-link will be used.
 - For count outcomes, the log-link will be used, and the follow-up time will be included as the offset in the model. (Poisson regression)
 - For time-to-event outcomes, we will use Poisson regression models, where the log-link will be used. The event indicator (1: event, 0: censoring) will be the response variable. Exposure time (i.e., days from the start date of the follow-up to either the date of the event occurrence or the end of follow-up, whichever comes first) will be included as the offset in the model.
- Treatment effect metrics
 - Following the recommendation of the CONSORT guideline,⁷ we will report the treatment effect in both absolute and relative metrics.
 - For binary outcomes, we will report odds ratio (OR) derived from the GLMM with the logit-link. In addition, we will calculate absolute difference (AD), using the resulting GLMM with G-computation. Bootstrap will be used to obtain a standard error for the estimated AD.
 - For count outcomes and time-to-event outcomes, we will report the incidence rate ratio (IRR) derived from the GLMM model. In addition, we will calculate absolute difference in incidence rate (i.e., incidence rate difference;IRD) in a similar way to calculate AD.
- Secular trend
 - Primary: Calendar time of the start date of the follow-up of each episode will be included as a continuous variable with natural cubic spline with 3 knots
 - Secondary: Period in which the trigger event occurs will be included as a categorical variable.
- Site (cluster)

- Since there are only 6 sites in this study, the conventional analysis of including cluster as random-effects is problematic due to this small number.¹⁰
- Primary: The primary analysis includes sites as fixed effects.
- Secondary: Sites will be included as random-effects with a small sample adjustment (the Kenward-Roger method).^{11,12}
- Subjects
 - We will potentially have more than one data point from one subject in this study.
 - To take account of within-subject correlation, subjects will be included as random effects.
 - The primary analysis will consider random intercepts only.
- Variables to be included the GLMM
 - **Table 8** lists the variables selected based on the study design (Category A) and clinical importance (Category B and C).
 - The primary analysis includes the variables in Category A and B.
 - As a secondary analysis, we will perform the same analysis including Category A, B and C.

Table 8: Variables that will or may be included in the generalized linear mixed-effects model for the primary analysis

Variable	Category A	Category B	Category C
Intervention indicator: (eSyM+ vs. eSyM-)	X		
Cohort (MO vs. Surgery)	X		
Calendar Time (Secular trends) [continuous with natural cubic spline]	X		
Site (Treating Facility) (DFCI, MMC, DHMC, LCI, BAPT, WVU) [as fixed effects]	X		
Interaction between Cohort (MO vs. Surgery) and Calendar Time (Secular trends)	X		
Interaction between Cohort (MO vs. Surgery) Site (Treating Facility) (DFCI, MMC, DHMC, LCI, BAPT, WVU) [as fixed effects]	X		
Subjects [as random effects (random intercepts only)]	X		
Goal of Chemotherapy (MO with curative goal, MO with palliative goal, Others)		X	
Age (years) (fractional polynomials)		X	
Sex (male vs. female)		X	
Race/Ethnicity (white/non-Hispanic, black/non-Hispanic, Hispanic, Other/Unknown)		X	
Rurality based on zip code (large metro, small metro, suburban, rural)		X	
Cancer/procedure type (GI, Gyn, Thoracic)		X	
Employment (Employed, Disabled, Retired, Other)			X
Marital status (Married vs. Not married)			X
Insurance type (Medicare only, Medicare and Medicaid, Medicaid only, Private, Other)			X
Socio-economic status (quintiles by the zip code-based poverty level)			X
Co-morbidity (Charlson comorbidity index from encounter diagnoses in the 12 months before the first eligibility date) (0, 1, 2+)			X

- Time decay of the intervention effect

- As a sensitivity analysis, we will include the interaction between the intervention and time from the rollout of the intervention condition at the treating site to the time of the trigger event, where we treat the time as a categorical variable in the model.

Considerations on the potential informative censoring

- Death is a competing event for EDTR and Hospitalization. In the primary analyses for EDTR and Admission, those who die without EDTR or Hospitalization will not be excluded from the analyses but included in the denominator when calculating the EDTR rate and Admission rate. Caution should be exercised in interpreting the intervention effect on these non-fatal outcomes. Because those who die before these non-fatal events will never experience it, the intervention effect on these non-fatal events will be biased in favor of either the control or intervention group where more deaths are observed. Therefore, when assessing the effectiveness of the intervention, we will also consider its impact on reducing death (a secondary outcome; see Table 5).
- As a sensitivity analysis for concluding the effectiveness of the intervention, we will analyze the composite of EDTR, Hospitalization, or Death event occurrence status at Day 30 (a secondary outcome; see Table 5), which is not subject to the competing risk problems.

Handling of potentially differentiable follow-up duration across episodes:

- While the planned follow-up duration for each episode is one-year, the actual follow-up durations of some episodes will be shorter than one year due to the occurrence of another trigger event or lost-to-follow-up during the one-year follow-up. Thus, the follow-up duration will be different across the episodes.
- For binary outcomes (i.e., the event status yes/no), the length of follow-up time will not be considered in the analysis. We expect that this will not affect the analysis of the primary endpoint (EDTR at Day 30) because we expect that we will have at least 30 days of follow-up for all episodes. The potential reason of censoring of follow-up is the occurrence of another trigger event during the follow-up time. It is unlikely for a patient to have another trigger event within 30 days after the previous trigger event.
- For count data, we will take the length of the follow-up period for each episode into account. Specifically, we will use Poisson regression models, where the logarithm of follow-up duration of each episode will be included as offset in the models.

